11.1.2. Overall Tumour Response (=Primary tumour and Metastatic lesions)

The overall response assessment takes into account the response in the primary tumour and metastases according to the criteria in the table below. The overall response assessment is shown in the last column, and depends on the assessments of the response in the primary tumour, target and non-target lesions, and the development of new lesions.

Primary Tumour	Target Lesions	Non-Target Lesions	New Lesions	Overall Response
CR	CR	CR	No	CR
CR	CR	Incomplete response/SD	No	PR
PR	PR	Non-PD	No	PR
Minor PR	Non-PD	Non-PD	No	Minor PR
SD	SD	Non-PD	No	SD
Any	PD	Any	Yes or No	PD
Any	Any	PD	Yes or No	PD
Any	Any	Any	Yes	PD

If a patient has not tumor evaluation due to clinical disease progression, it will be classified as a progressive disease.

11.1.3. Objective tumour response and progression

Primary efficacy endpoint

The primary efficacy endpoint is defined as the proportion of patients who had a documented complete or partial tumour response occurring after the first 2 cycles of treatment which must be confirmed by a follow-up objective tumour assessment obtained within 4-5 weeks after the initial documentation.

Secondary endpoints

Secondary efficacy endpoints are defined as follows:

- The best overall response is the best response recorded from the start of the treatment until disease progression/recurrence (taking as reference for PD the smallest measurements recorded since the treatment started) over the whole treatment duration. It must be confirmed by a follow-up objective tumour assessment obtained within 4-5 weeks after the initial documentation.
- Duration of tumour response: the time from first documentation of objective tumour response to the first objective or clinical documentation of progression
- Time to treatment failure: the time from the date of first treatment administration to the first documentation of tumour progression, discontinuation of study treatment before one year, or death, whichever occurs first
- Progression-free survival (PFS): the time from the date of first treatment administration to the date of first objective or clinical documentation of tumour progression or death due to any cause
- Overall survival (OS): the time from the date of first treatment administration to date of death

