9. TREATMENT ADMINISTRATION

9.1. Starting doses and schedules

ARM A		
D1 and D8 Vincristine	1.5 mg/m ² /d – IV bolus (0.05 mg/kg for patient ≤ 10 kg)	3 weekly
D1 to D5 Irinotecan	50 mg/m ² /d – IV over 1 hour	3 weekly
ARM B		
D1 to D5 Temozolomide	125 mg/m ² /d - PO	3 weekly
D1 and D8 Vincristine	1.5 mg/m ² /d – IV bolus (0.05 mg/kg for patient ≤ 10 kg)	3 weekly
D1 to D5 Irinotecan	50 mg/m ² /d – IV over 1 hour	3 weekly

Vincristine: The dose of vincristine will be 1.5 mg/m² or 0.05 mg/kg for patient ≤ 10 kg (maximum 2.0 mg) and will be administered by direct intravenous infusion on day 1 and day 8 of each course, before irinotecan. Administration must comply with guidance on administration of vinca alkaloids as per NPSA/2008/RRR004.

Irinotecan: The dose of irinotecan will be 50 mg/m²/day. Irinotecan will be given intravenously infusion over 1 hour on days 1-5, one hour following the administration of TMZ. In absence of contraindications (known allergies), **systematic treatment with oral cefixime 8 mg/kg once a day (maximum daily dose 400 mg) is recommended and will be started 2 days before chemotherapy until day 7** (see Appendix 11 for cefixime management in The Netherlands).

Temozolomide: will be given according to the randomization: The starting dose of TMZ will be 125 mg/m²/day. The dose of TMZ will be escalated to 150 mg/m²/day at cycle 2 for patients who do not experience ≥ grade 3 toxicity of any kind. The dose of TMZ should be rounded to the nearest 5 mg. TMZ will be given orally, on an empty stomach, prior to vincristine and irinotecan, on days 1-5 repeated every 3-weeks. If the patient vomits within 20 minutes after TMZ, the dose will be re-administered. The capsules must be swallowed whole with a glass of water. For young children and patients who have difficulty swallowing capsules, the full daily dose of TMZ capsules should be placed

in 10-30 ml fruit juice or compote and administered after the capsules have been allowed to soften for 15-20 minutes or according to normal local practice for patients in the United Kingdom (see Appendix 12).

Treatment will continue until disease progression, unacceptable toxicity or the patient's desire to discontinue therapy. Local treatment is allowed after 2 cycles.

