Patients must have evidence of recovery from all prior cycle toxicity and the ANC must be > 1000/mm³ and platelets > 100 000/mm³ before receiving the next cycle of therapy. If initiation of the next treatment cycle is delayed by more than 2 weeks, the patients should be discontinued from the study.

In the absence of clinically progressive disease, patients should receive at least 2 cycles of VIT or VI prior to the first evaluation on study treatment.

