10.2.2 Treatment procedures for subsequent cycles

The following procedures must be performed prior to dosing with Temozolomide in combination with Vincristine and Irinotecan on the days indicated during weeks through all subsequent weeks that patient remains on study treatment (days 1, 8 and 15 based on 21 day cycles). Blood sampling will be made after application of topical anaesthetic cream, where appropriate.

Type of Assessment	Delay for subsequent cycles

CLINICAL EXAM
 
 • Full physical examination • height, weight , body surface • Vital signs : blood pressure after 5 min at rest, heart rate, temperature • Performance status (Lansky Play Score or Karnofsky Score – appendix 3-4) • Assessment of adverse events according to the NCI-CTC AE v.4.0 (appendix 5) • Recording of concomitant medications 	
day 1

LABORATORY TESTS
 
 • Complete blood count : white count (WBC), hemoglobin (HGB), hematocrit (HCT), differential count and platelet count 	
days 1, 8, 15.
 
If aplasia, blood counts should be performed as clinically indicated

 • Blood chemistry : glucose, creatinine, electrolytes (sodium, potassium, chloride and bicarbonate), AST, ALT, total and direct bilirubin, ASAT-ALAT, creatinine 	
day 1 if normal during cycles 1 and 2.
 
If significantly abnormal during cycle 1 or 2, blood chemistry should be taken on days 1, 8 and 15 for all subsequent cycles after cycle 2

RADIOLOGICAL AND OTHER INVESTIGATIONS
 
 • Tumor assessments (CT scan and/or MRI) including measurement of target lesion and assessment of response to treatment should be loaded the CDs onto the PACS system for later review. • Bone scan or FDG-PET Scan* • BM aspirates and trephine biopsies* 	
Mandatory after completion of every two cycles (must assess at 5 weeks after cycle 2 for responding or stable disease)

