10.2.3 End of study treatment / Withdrawal procedures

The duration of study participation is a maximum of 12 cycles. However, the continuation of treatment can be individually discussed with the investigator for patients who do not experience progression of disease after 12 cycles.

The following evaluation is performed 3 weeks after the last cycle of chemotherapy or at the end of study (see 7.2.).

Type of Assessment	Delay for End of Study treatment or Withdrawal

CLINICAL EXAM
 
 • Full physical examination • height, weight, body surface • Vital signs : blood pressure after 5 min at rest, heart rate, temperature • Performance status (Lansky Play Score or Karnofsky Score – appendix 3-4) • Assessment of adverse events according to the NCI-CTC AE v.4.0 (appendix 5) • Recording of concomitant medications 	
To be performed 3 weeks after the last cycle of chemotherapy or at the end of study

LABORATORY TESTS
 
 • Complete blood count : white count (WBC), hemoglobin (HGB), hematocrit (HCT), differential count and platelet count • Serum chemistries : glucose, urea, creatinine, total protein, albumin, Ca+, phosphorus and electrolytes (sodium, potassium, chloride and bicarbonate), AST, ALT, total bilirubin, alkaline phosphatase, LDH, GGT 	
To be performed 3 weeks after the last cycle of chemotherapy or at the end of study

RADIOLOGICAL AND OTHER INVESTIGATIONS
 
 • Tumor assessments (CT scan and/or MRI) including measurement of target lesion and assessment of response to treatment should be loaded the CDs onto the PACS system for later review. • Bone scan or FDG-PET Scan* • BM aspirates and trephine biopsies* 	
Mandatory
 
To be performed 3 weeks after the last cycle of chemotherapy or at the end of study, except documented previous disease progression

**only repeated if clinically indicated or if initially involved or to confirm tumor response*

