10.2.4 Follow-up visit

Patients will be followed every 3 months for at least 2 years and then every 6 months during the subsequent 3 years or until death or lost to follow up until the date of the study cut-off, for the following:

- Patient status determination
- Tumour assessments including measurement of target lesion and assessment of response to treatment should be loaded the CDs onto the PACS system for later review.

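### A cycle-2 responder who stops treatment right after cycle 2 has no scheduled scan in the 4-5 week window that the primary endpoint requires for confirmation

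*Protocol*

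**What the plan says.** Protocol 11.1.3 defines success as a complete or partial response after the first two cycles, "which must be confirmed by a follow-up objective tumour assessment obtained within 4-5 weeks after the initial documentation". Nothing in that definition makes confirmation depend on continued treatment.

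The matching scan is in 10.2.2, where the imaging row adds "must assess at 5 weeks after cycle 2 for responding or stable disease". That table applies "through all subsequent weeks that patient remains on study treatment". Appendix 2 repeats the requirement, as 4-5 weeks after cycle 2, in a footnote to its subsequent-cycles column.

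Off treatment, 10.2.3 makes one scan mandatory: "To be performed 3 weeks after the last cycle of chemotherapy or at the end of study, except documented previous disease progression". After that, 10.2.4 applies: "Patients will be followed every 3 months for at least 2 years", with tumour assessments at those visits.

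Several routes lead off treatment after cycle 2. Section 7.8 lists toxicity, patient request, investigator decision and delay. On delay, 9.1 says: "If initiation of the next treatment cycle is delayed by more than 2 weeks, the patients should be discontinued from the study". Section 9.1 also says "Local treatment is allowed after 2 cycles".

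For the denominator, 12.2 calls a patient evaluable for the main objective on two cycles and an available cycle-2 tumour evaluation. It does not ask for a confirmation scan.

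**The concern.** The endpoint asks every cycle-2 responder for a second scan in a narrow window, but the visit schedule provides that scan only for those who continue treatment. A responder who stops straight after cycle 2 keeps a place in the denominator and, without an unscheduled scan, does not meet the success definition even if nothing has progressed.

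The loss can fall only on responders, so it pushes the response rate in one direction, down. The decision rule has limited slack: success in the VIT arm needs 22 of 47, against an expected 25.85 at the design rate. An analysis plan can say how to score a missing confirmation, but it cannot supply a scan that the protocol did not schedule.

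**Working it through.** **Scan timing.** Inputs: 21-day cycles (9.1), no delays, cycle 2 starting on day 22 and ending on day 42. The first response scan is taken on day 42, or as early as day 36 (assumption). The confirmation window is 28-35 days later. Section 10.2.3 does not say from which day its 3 weeks run, so four readings are shown.

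Patient who stops after cycle 2:

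| 3 weeks counted from | End-of-treatment scan | Days after day-42 scan | Days after day-36 scan |
|---|---|---|---|
| Start of cycle 2 (day 22) | day 43 | 1 | 7 |
| Last irinotecan (day 26) | day 47 | 5 | 11 |
| Day-8 vincristine (day 29) | day 50 | 8 | 14 |
| End of cycle 2 (day 42) | day 63 | 21 | 27 |

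No entry reaches 28 days.

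The first 3-monthly visit is far too late. Taking 3 months as 91 days and counting even from day 29, it falls on day 29 + 91 = 120, which is 120 - 42 = 78 days after a day-42 scan.

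The delay route ends in the same place. Cycle 3 is due on day 43, and a delay of more than 14 days takes the patient off treatment after day 57. The window for a day-42 scan is days 70-77.

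Patient who stops after cycle 3: the same four readings give scans on days 64, 68, 71 and 84. These are 22, 26, 29 and 42 days after a day-42 scan (one of four in the window), or 28, 32, 35 and 48 days after a day-36 scan (three of four in the window). The certain gap is therefore the stop right after cycle 2.

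**The plan's own figures.** For p0 = 0.35, p1 = 0.55 and alpha = beta = 0.10 (12.1, revised design), an exact search for the Simon optimum gives a total of 47, which reproduces the stated number. The stated rule, read as a single stage, gives:

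- P(X >= 22 | n = 47, p = 0.35) = 0.063
- P(X >= 22 | n = 47, p = 0.55) = 0.899

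**Effect of lost confirmations.** Let f be the share of true responders left without in-window confirmation. It is not in the documents and is assumed. The observed success rate is 0.55 x (1 - f), and the chance of success is P(X >= 22 | n = 47, that rate).

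| f | Observed rate | P(at least 22 of 47) |
|---|---|---|
| 0 | 0.550 | 0.899 |
| 5% | 0.5225 | 0.814 |
| 10% | 0.495 | 0.696 |
| 15% | 0.4675 | 0.554 |
| 20% | 0.440 | 0.403 |

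Expected responders are 47 x 0.55 = 25.85. Losing two of them (f = 2/25.85 = 7.7%) gives 0.753. The expected count falls to the cut-off at f = 1 - 22/25.85 = 14.9%.

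**The case against.** The strongest reply is that the endpoint definition itself requires the confirming scan, with no on-treatment condition, and that nothing forbids taking one off schedule. Section 13.9 collects imaging until progression, not until treatment stops. In 10.2.3 a footnote foresees bone scan, PET or marrow repeated to confirm response. This stands in part. It rules out saying that such a patient cannot be confirmed; the accurate statement is that no scan is scheduled in the window.

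A reader might also infer that local treatment as such takes responders off the confirmation schedule. The current text does not support that. Version 5.1 removed local therapy after the second cycle as a withdrawal criterion, and 7.8 no longer lists it. A patient who resumes within the delay limit stays on the 10.2.2 schedule. Local treatment leads to the gap only through a delay of more than 2 weeks or another listed reason. If the patient stays on schedule, the difficulty is a different one: a scan after surgery or radiotherapy no longer shows drug response alone. Nor does the version 5.1 note show that confirmations are being missed. It concerns explaining the overall survival effect.

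On size, the objection has force. The loss share is assumed. The protocol does not say whether 0.55 is a rate before or after confirmation; if it already allows for unconfirmed responses, the table counts part of the loss twice. Section 12.2 treats the cut points as guidelines, weighed with the VI response rate, toxicity and external evidence, so missing 22 does not by itself reject VIT.

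Finally, scoring an unconfirmed response as a failure is the usual conservative result of a confirmed endpoint, and detailed handling may be in an analysis plan not shown. That answers the scoring question but not the missing scan.

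**Conclusion.** The gap is real and narrow. A cycle-2 responder who stops right after cycle 2 has an end-of-treatment scan that is too early to confirm and follow-up scans that are too late, yet stays evaluable. Without an unscheduled scan the patient is not a success, which biases the response rate down.

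If 0.55 is the rate before this loss and 5-10% of responders are lost, the observed rate falls by 2.75 to 5.5 percentage points, and the chance of reaching 22 of 47 falls from 0.899 to between 0.81 and 0.70. Both conditions are assumptions; the documents give no frequency.

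A reader might go further and infer that the loss is greater under VIT and so shrinks the VIT-VI difference. Unequal loss would distort that difference, but nothing in the protocol shows that the loss differs by arm.

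**What to change.** In 10.2.3 and Appendix 2, state that any patient with a complete or partial response at cycle 2 has a tumour assessment 4-5 weeks after first documentation, whether or not study treatment continues. Do this by re-timing the end-of-treatment scan that is already mandatory.

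Keep the confirmed-response definition in 11.1.3 for the primary analysis. Counting an unconfirmed cycle-2 reading as a primary success would redefine the endpoint, against 11.1.1 (responses must last at least 4 to 5 weeks) and 11.1.3, in an open-label trial whose first 80 patients have already been reviewed. Instead, report by arm the number of cycle-2 responders without in-window confirmation or with local treatment before it, and add a sensitivity analysis that counts their centrally read cycle-2 response.

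The cost is wording in two places and one extra analysis, with no added scan. The downside is a later end-of-treatment scan for these patients. With a day-42 cycle-2 scan it moves from between day 43 and day 63 to days 70-77, that is 7 days (70 - 63) to 34 days (77 - 43) later, depending on how the present 3 weeks are counted.

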Most patients with relapsed rhabdomyosarcoma have measurable disease at local and/or metastatic sites at relapse. In this study we will test the new combination of vincristine, irinotecan and TMZ in RMS, using objective volumetric response after 2 cycles of treatment as our primary endpoint.

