A clinical assessment should be done at each visit in order to detect tumour progression at any point during treatment. This should be supplemented by radiological examination as appropriate.

RELATIONSHIP BETWEEN CHANGE IN SINGLE DIAMETER (RECIST), PRODUCT OF TWO DIAMETERS (WHO), AND THREE PERPENDICULAR DIAMETERS ("VOLUME")

	Diameter, 2R	Product,(2R) ²	Volume, 4/3πR ³
Response	Decrease	Decrease	Decrease
	13%	24%	33%
	30%	50%	65%
	50%	75%	87%
Disease Progression	Increase	Increase	Increase
	12%	25%	40%
	20%	44%	73%
	25%	56%	95%
	30%	69%	120%

Response evaluation criteria (Volumetric)

Complete Response (CR)	Complete disappearance of all visible disease
Partial Response (PR>2/3)	≥ 65% reduction of tumour volume (volume response between 65-99%)
Minor Partial Response (PR<2/3)	Volume response between 34-64%
Stable Disease (SD)	No criteria for PR or PD
Progressive Disease (PD)	Any increase of more than 73% of any one target lesion/tumour volume or appearance of new lesions.

All responses must last at least 4 to 5 weeks without evidence of tumour progression or relapse.

Metastatic Disease Measurement

The RECIST 1.1 (*European Journal of Cancer 2009; 45: 228–47*) criteria will be used for assessment of the size of measurable metastases, including nodal metastases.

RECIST Methodology

Planes and techniques:

- CT: The same method of assessment and the same technique should be used to characterize each identified and reported lesion at baseline and during follow-up. Lesions should be measured on the same window setting on each examination.
- MRI: Lesions must be measured in the same anatomic plane by use of the same imaging sequences on subsequent examinations.

Measurements:

DIAGNOSIS

- **Measurable lesion:** A lesion that can be accurately measured in at least 1 dimension with the longest diameter at least twice the thickness of the CT or MR slice with a minimum of 10 mm (for lymph nodes ≥15 mm shortest axis). This is defined as a "**target lesion**". The investigator will identify up to 5 target lesions total and up to 2 per organ to be followed for response. In general, the largest lesions representative of involved organs are selected to follow as target lesions. However, in some cases, the largest lesions may not be easily measured and are not suitable for follow-up because of their configuration. In these cases, identification of the largest most reproducible lesions is advised. Serial measurements of

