The main analysis will be performed on the intent to treat principle, considering all patients included in the study. Patients who withdraw from the study will be accounted for up until the time they withdraw from the study. Secondary analyses will be performed on the per protocol population, that is eligible, evaluable and treated patients. Safety analyses will be performed on all treated patients. Eligible patients are defined as patients who did not have a major violation of eligibility criteria (inclusion and exclusion criteria).

Treated patients are defined as patients who received at least one injection of the study treatment.

Evaluable patients for main objective (objective response at 2 cycles) are defined as patients who received at least 2 cycles of the study treatment and whose the tumor evaluation at 2 cycles was available.

The estimated difference in response rates between the two arms, will be presented with a 90% confidence interval. A Bayesian analysis of the final data will also be performed in which probabilities that one arm is better than the other will be given.

The risk / benefit ratio will be examined biannually by the IDMC on validated data. The sponsor may decide to temporarily halt recruitment to the trial if the rate of severe toxicities significantly exceeds 15%.

The decision rules for early termination are applied to the VIT arm as the VI arm is only used for controlling selection bias. However, at the end of the trial, if the VIT arm is considered sufficiently active, a phase III trial may be initiated. If the VIT arm is considered insufficiently active, this treatment strategy is rejected and other options should be considered. The cut points for acceptable and unacceptable response rates, obtained from the Optimum Simon design, will be used as guidelines for deciding whether VIT is worthy of further investigation; the response rate in the VI arm, the toxicity of the regimens and relevant external evidence will also be taken into consideration. Categorical variables will be presented as frequencies and percentages. Continuous variables will be presented as means (standard deviation), and medians (range). The treatment groups will be compared for demographic and initial disease characteristics using Fisher's exact test for categorical variables and the non-parametric Wilcoxon test for continuous variables.

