Appendix 2 – Flowchart

	Inclusion 7 days < TTT	First 2 cycles	Subsequent cycles	End of study (10)	Follow-up (11)
		during weeks 1-6			
Information and consent form signed	X				
Diagnosis, medical/oncology history and demographics All clinical signs	X				
CLINICAL EXAM					
Full Physical examination, weight, height, body surface, performance status	X	X at day 1	X	X	X
Vital signs (body temperature, systolic and diastolic blood pressure sitting after 5 minutes rest, heart rate after 5 minutes rest, respiration rate)	X	X	X	X	
Concomitant treatment		X	X	X	
LABORATORY TESTS (1)					
Complete blood count	X	X (5,6)	X (5,6)	X	
ASAT, ALAT, total bilirubin, alkaline phosph, LDH, GGT	X	X (5)	X (8)	X	
Iono (Electrolytes), urea, creatinine, total protein, glucose, calcium, phosphate, albumin, chloride and bicarbonate	X	X (5)	X (8)	X	
Serum or urine pregnancy test, if applicable	X				
TUMOR ASSESSMENT (2)					
Computed Tomography (CT) scan or MRI of the primary site (3) Bone scan or FDG-PET Scan recommended BM aspirates, trephines biopsies recommended mandatory in case of bone marrow disease	X (4)	X (2,3,7)	X (2,3,9)	X (2,3)	X (2,3,12)
SAFETY ASSESSMENT					
Adverse events		X	X	X	X

- (1) All blood sampling will be done after local application of topical anaesthetic cream, if applicable
- (2) All imaging data should be stored in DICOM format for further review on CD-Rom
- (3) Volume estimation should be attempted by providing the maximum sagittal, coronal and axial diameters. For MRI, intravenous gadolinium administration is mandatory for all MRI examinations (post-contrast T1-weighted sequences should ideally be performed with saturation). MRI is particularly recommended for

limb, head/neck, pelvis and paraspinal masses. MRI appears to be superior to CT scan in defining soft tissue extension. CT Scan could be performed for the assessment of thoracic or abdominal tumors.

- (4) Within 14 days prior to the first study drug dose
- (5) On days 1, 8 and 15
- (6) If aplasia, blood counts should be performed as clinically indicated
- (7) After cycle 2
- (8) At day 1 if normal during cycles 1 and 2. If significantly abnormal during cycles 1 and 2, blood chemistry should be taken on days 1, 8 and 15 for all subsequent cycles after cycle 2
- (9) After completion of every two cycles (must assess at 4-5 weeks after cycle 2 for responding or stable disease)
- (10) 3 weeks after the last cycle of chemotherapy or at the end of study

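### Best overall response must be confirmed within 4-5 weeks, but routine scans are six weeks apart, so a response first seen after cycle 4 or later has no scheduled scan that can confirm it

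*Protocol*

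**What the plan says.** Section 11.1.3 of the protocol defines two response endpoints with the same confirmation rule.

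- **Primary endpoint:** complete or partial response after the first two cycles, "confirmed by a follow-up objective tumour assessment obtained within 4-5 weeks after the initial documentation". Section 5.1 ("using objective volumetric response after 2 cycles of treatment as our primary endpoint") and the analysis part of section 12 ("Evaluable patients for main objective (objective response at 2 cycles) are defined as patients who received at least 2 cycles of the study treatment") tie it to the cycle-2 assessment.
- **Best overall response (secondary):** the best response recorded "over the whole treatment duration. It must be confirmed by a follow-up objective tumour assessment obtained within 4-5 weeks after the initial documentation".

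Three other places bear on the interval.

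- **Section 10.2.2** sets imaging as "Mandatory after completion of every two cycles (must assess at 5 weeks after cycle 2 for responding or stable disease", with days "based on 21 day cycles".
- **Appendix 2, note 9** repeats the two-cycle rule but gives a different time for the extra check: "must assess at 4-5 weeks after cycle 2 for responding or stable disease".
- **Section 11.1.1**, under the volumetric criteria: "All responses must last at least 4 to 5 weeks without evidence of tumour progression or relapse".

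**The concern.** The confirmation rule has an upper limit of five weeks. Apart from one check after cycle 2, the imaging calendar has a six-week step. For an endpoint that runs over as many as 12 cycles, the rule and the calendar do not fit together once the first response appears after cycle 4 or later. A response that is still present at the next planned scan would fail confirmation because of the scan date and not because the tumour grew.

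The interval is also stated in two directions. Section 11.1.1 gives a floor (the response must last at least so long). Section 11.1.3 gives a ceiling or window (the confirming scan must come no later than so long). A response first seen after cycle 4 and still present six weeks later satisfies the first and fails the second, so two analysts could classify the same patient differently.

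At stake is the classification of late responders in a listed secondary objective.

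**Working it through.** **Inputs**

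- Cycle length: 21 days (section 10.2.2).
- Routine imaging: after every two cycles (section 10.2.2; Appendix 2, note 9).
- Extra check: 5 weeks after cycle 2 (section 10.2.2), or 4-5 weeks after cycle 2 (Appendix 2, note 9).
- Confirmation limit: 4-5 weeks from first documentation, i.e. 28 to 35 days (section 11.1.3).
- Largest permitted delay: a patient whose next cycle is delayed by more than 2 weeks stops (section 9.1), so at most 14 days per cycle.
- Decision rule: at least 22 responses among 47 in the VIT arm, with p0 = 0.35 and p1 = 0.55 (section 12.1).

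**Step 1. The plan's own figures.** With X binomial(47, p), P(X ≥ 22) is 0.063 at p = 0.35 and 0.899 at p = 0.55. These agree with the stated alpha of 0.10 (not exceeded) and beta of 0.10. Neither figure depends on the confirmation interval.

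**Step 2. The on-time calendar**, in days from the start of treatment:

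| Assessment | Day |
|---|---|
| After cycle 2 | 2 × 21 = 42 |
| Extra check | 42 + 28 = 70 to 42 + 35 = 77 |
| After cycle 4 | 4 × 21 = 84 |
| After cycle 6 | 6 × 21 = 126 |
| After cycle 8 | 8 × 21 = 168 |

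**Step 3. Gap from first documentation to the next planned scan, for a patient who stays on treatment:**

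| Response first seen | Gap to planned scan(s) | Inside 28-35 days? |
|---|---|---|
| After cycle 2 (day 42) | 70 − 42 = 28 to 77 − 42 = 35 days | Yes |
| At the extra check (days 70-77) | 84 − 77 = 7 to 84 − 70 = 14 days; then 126 − 77 = 49 to 126 − 70 = 56 days | No |
| After cycle 4, 6, 8 or 10 | 42 days | No; 42 − 35 = 7 days late |

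If both cycles between two routine scans are delayed by the maximum, the gap is 42 + 2 × 14 = 70 days, which is 70 − 35 = 35 days late.

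**Step 4. Does the reading of *within* matter?** It can mean a window (28 to 35 days) or only a ceiling (any time up to 35 days). For a response first seen after cycle 4, 6, 8 or 10 the gap of 42 days fails under both. For a response first seen at the extra check, the scan 7 to 14 days later fails the window and passes the ceiling. Only the floor in section 11.1.1 accepts the 42-day scan.

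**Step 5. The primary endpoint.** The scheduled check lies 28 to 35 days after a cycle-2 scan taken on day 42, so no on-schedule confirmation is lost and the figures in Step 1 stand. The margin is thin in one place. The check is timed from cycle 2, while the window runs from first documentation. If the 5 weeks in section 10.2.2 are counted from the end of cycle 2 (day 77), a scan on day 41 gives 77 − 41 = 36 days, one day too many. The earlier end of the range in Appendix 2 gives 70 − 41 = 29 days, which fits.

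**The case against.** The strongest reply is that the protocol provides for what matters. The decision rule uses response after two cycles, and for that response a dedicated scan is mandated inside the window. Best overall response is only to be described, and no decision depends on it. A requirement to confirm can also be read as itself calling for a scan: nothing forbids an unscheduled one, and section 11.1.1 allows radiological examination as appropriate. Finally, the floor in section 11.1.1 can be read as a statement about durability and the window in section 11.1.3 as a statement about when to look, which together amount to re-scanning at about 4-5 weeks.

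Most of this stands. It limits the point to the secondary endpoint and to wording. It does not remove the mismatch: the calendar that sites follow contains no slot for the scan that the definition demands after cycle 4 or later, and the protocol does not say how a response still present at six weeks is to be scored.

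A reader might go further and infer that the primary response rate is biased downward and the 22-of-47 rule loses power. The arithmetic for that is easy: if 5%, 10% or 15% of responders missed the limit, 0.55 would become 0.5225, 0.495 or 0.4675, and power would fall from 0.899 to 0.814, 0.696 or 0.554. But those percentages are assumptions. The documents give no rate of late scans, and the schedule as written produces none. Such losses would be timing deviations and not a consequence of the plan.

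Nor do the documents support saying that late responses can never be confirmed, or that best overall response collapses to the cycle-2 response. Unscheduled scans are allowed, and under the ceiling reading a response first seen at the extra check is confirmed at day 84.

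**Conclusion.** The definition of best overall response does not fit the imaging calendar. For a patient who stays on treatment, a response first seen after cycle 4, 6, 8 or 10 has its next planned scan at 42 days or later, against a limit of 35. The protocol also states the interval as a minimum in one section and as a limit in another, and gives the post-cycle-2 check as 5 weeks in one place and 4-5 weeks in another.

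For the primary endpoint the finding is confined to wording. With an on-time cycle-2 scan, the scheduled check meets the window and the stated operating characteristics are unchanged.

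This rests on 21-day cycles given on time; a delay only lengthens the 42-day gap. The size of the effect on best overall response cannot be computed, because the documents do not say how many first responses occur after cycle 2. Severity is minor to moderate.

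**What to change.** **Best overall response (section 11.1.3).** Require confirmation by an assessment at least 4 weeks (28 days) after first documentation, and accept the next scheduled two-cycle assessment that meets this minimum. A response first seen after cycle 4 is then confirmed by the routine scan 42 days later. One first seen at the extra check is confirmed at day 126, since day 84 is too soon.

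**Primary endpoint.** Leave the scheduled check as it is and reconcile the text:

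- Give the same interval in section 10.2.2 and Appendix 2, note 9.
- State that the check is timed from the cycle-2 scan, so that it and the window in section 11.1.3 run on one clock.
- State how the minimum duration in section 11.1.1 and the window in section 11.1.3 work together, and how a response whose next scan falls outside the window is scored.

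**Cost.** No extra scans are needed, and no treatment rule or sample-size figure changes. The change to best overall response does alter which patients count as responders, and it comes after the IDMC has reviewed the first 80 patients. It should therefore be documented and dated before the blinded central review (section 13.9) classifies responses, with best overall response also reported under the existing rule so that readers can see the difference. Whether it needs a formal amendment is to be judged under section 13.4.
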